3.0 Introduction

This analysis plan describes the statistical analyses to be completed by AbbVie Data and Statistical Science for ABBV-8E12 Study Protocol M15-570, that incorporates one amendment (original Protocol: 09 April 2018; Amendment 1: 24 January 2019; Amendment 2: 20 October 2020).

This statistical analysis plan (SAP) provides details to further elaborate statistical methods as outlined in the protocol and describes analysis conventions to guide the statistical programming work. Population pharmacokinetic and exposure-response analysis for this study will be conducted separately and are not included in this SAP. The SAP v2.0 is updated to provide details of analysis for the abbreviated CSR.

Analyses will be performed using SAS version 9.3 or higher (SAS Institute Inc., Cary, NC 27513) under the UNIX operating system.

4.0 Study Objectives, Design and Procedures

4.1 Objectives

The primary objective of this study is:

- To assess the long-term safety and tolerability of ABBV-8E12 in subjects with early Alzheimer's disease (AD).

The secondary objective of this study is:

- To assess the pharmacokinetics (PK) of ABBV-8E12 in subjects with early AD.

The exploratory objectives of this study are:

- To assess the long-term efficacy of ABBV-8E12 in slowing disease progression in subjects with early AD.

- To assess the long-term effect of ABBV-8E12 on a range of disease-related and drug-related biomarkers in subjects with early AD.

4.2 Study Design

This Phase 2 extension of a multiple dose, multicenter, multinational, double-blind study is designed to evaluate the long-term safety and tolerability of ABBV-8E12 in subjects with early AD. The study will consist of a 5-year treatment period and a follow-up period of approximately 20 weeks following the last study drug administration.

All subjects who complete the Treatment Period in Study M15-566 will be eligible to participate in this study according to the selection criteria. Upon completion of baseline study procedures, eligible subjects will receive ABBV-8E12 via intravenous (IV) infusion on Day 1 of Study M15-570 as follows:

- Subjects who received placebo in Study M15-566 will receive 2000 mg ABBV-8E12 in Study M15-570;
- Subjects who received 300 mg ABBV-8E12 in Study M15-566 will receive 1000 mg ABBV-8E12 in Study M15-570; and
- Subjects who received 1000 mg or 2000 mg ABBV-8E12 in Study M15-566 will continue on the same dose in Study M15-570.

Note: if any changes are made to alter Study M15-566 with regards to the treatment arms due to safety, efficacy, or other reasons, a corresponding change will be implemented in Study M15-570. This change may include, but is not limited to, adding or dropping treatment arm(s).

Subjects will receive study drug infusion every 4 weeks and undergo other study procedures and assessments as outlined in the Study Activities table ([Table 2](#)). Subjects will continue to receive treatment until one of the discontinuation criteria is met, the sponsor discontinues the study, or the subject completes the 5-year treatment period of Study M15-570.

[figure not shown]
Day 1 visit of Study M15-570 (day of the first dose of Study M15-570) will be at least 4 weeks but no more than 8 weeks after the last dosing visit (Week 92) of Study M15-566. Should this window be longer than 8 weeks, the subject may be considered for participation in Study M15-570 only with the approval of the therapeutic area medical director (TA MD). The investigators and subjects will remain blinded to the treatment assignments in Study M15-566 and will be blinded to the dose level of ABBV-8E12 in Study M15-570.

For subjects who do not have extended interruptions in study drug administration between Study M15-566 and Study M15-570 (i.e., the duration between the last dose of study drug in Study M15-566 and the first dose of study drug in Study M15-570 is no more than 8 weeks), certain procedures that were performed at the Week 96 Visit in Study M15-566 do not need to be repeated for the Day 1 Visit in Study M15-570.

Safety will be closely monitored during the study conduct. The study will also utilize an external data monitoring committee (DMC), which will review accumulating study data and make recommendations based on the emerging safety profile of ABBV-8E12. The DMC membership, responsibilities, operating logistics, and timing of reviews will be documented in a charter that will be finalized prior to the first DMC review meeting.

A schematic of the study design is shown in [Figure 1](#).

Figure 1. Study Schematic

4.3 Sample Size

The sample size for this study is dependent on the number of subjects who complete Study M15-566 and are qualified for enrollment into Study M15-570. Enrollment of Study M15-566 has been completed with 453 subjects randomized. The number of subjects who enroll in Study M15-570 could be up to 453.

4.4 Interim Analyses

Interim Efficacy Analysis

No interim analysis will be performed due to early termination of the study.

Safety Reviews

The DMC for Study M15-566 will serve as the DMC for Study M15-570. Before database lock of Study M15-566, DMC safety reviews of Study M15-570 data will follow the same schedule as the Study M15-566 DMC safety review meetings (i.e., data from both studies will be reviewed jointly depending on the pre-specified Study M15-566 review time points). The database snapshots will be taken for the safety interim reviews.

Once the database is locked for Study M15-566, there will be no further planned DMC reviews for Study M15-570.

4.5 Safety Variables

The following safety evaluations will be performed and safety information will be collected during the study: Adverse event, vital signs, ECG, laboratory tests, C-SSRS, and MRI assessments, and immunogenicity as determined by ADA responses in blood.

4.6 Biomarker and Pharmacogenetic Research Variables

4.6.1 Biomarker Research Variables

Plasma and Optional CSF Concentration Variables

CSF samples will be assayed for free and total tauA value for the ratio of free tau concentration to total tau concentration could be determined The assessments on free tau and the ratio of free tau to total tau could be done to investigate the binding of ABBV-8E12 to tau. CSF samples will also be analyzed for neurofilament light chain (NFL). Plasma samples will be assayed for total tau and NFL.

Volumetric MRI

Baseline volumetric MRI (vMRI) measurements and measurements on change from baseline in vMRI measurements will be obtained. The baseline measurement will be the same as the baseline measurement for Study M15-566, that is, the last measurement obtained before the first study drug administration of Study M15-566. Measurements will be obtained for whole brain, hippocampus, and lateral ventricles. Measurements may be obtained for additional regions.

Tau PET Imaging

The amount of tau deposits in a given region will be assessed by calculating a standardized uptake value ratio (SUVR) of each region. The SUVR is a ratio between the standardized uptake values (SUV) of a target brain region relative to that of cerebellar

cortex, which is considered as the reference tissue devoid of tau. The SUV is calculated by normalizing the concentration of radioactivity in the region (KBq/mL) to the injected dose (BMq) and the subject's body weight (kg). Additional variables (e.g., proportion of voxels within a target region that have a SUVR greater than a predetermined cutoff value) that reflect the extent or spread of tau pathology might also be assessed. Due to the exploratory nature of these PET imaging endpoints, values will be obtained for multiple brain regions, which will include, but not necessarily be limited to, 4 composite meta-regions that correspond to anatomical definitions of Braak stages III, IV, V, and VI.

5.0 Analysis Populations and Analysis Data Set

Data Sets for Safety Analyses

Safety Data Set: The Safety Data Set will contain data from Study M15-570 only, regardless of the treatment received in Study M15-566. Baseline for the Safety Data Set will be the last observation on or before the first dose of ABBV-8E12 in Study M15-570. If no Baseline is recorded in Study M15-570, the last value in Study M15-566 will be used as the Baseline.

6.0 Demographics, Baseline Characteristics, Subject History, and Previous/Concomitant Medications

The data analysis will be conducted on Safety Data Set and among treatment groups defined as Studies M15-566/M15-570: 300/1000 mg, 1000/1000 mg, placebo/2000 mg, and 2000/2000 mg.

6.1 Demographic and Baseline Characteristics

The following demographic and baseline characteristics will be summarized for each treatment group.

- Gender (male/female)
- Race (white, black, American Indian/Alaska native, Native Hawaiian or other Pacific Islander, Asian, Other, Multi-Race)

- Education (high school or above, lower than high school)
- Ethnicity (Hispanic or Latino)
- Age (years)
- Age group (<65, ≥ 65)
- Weight for all subjects (kg)
- Weight for all male subjects (kg)
- Weight for all female subjects (kg)
- Height (cm)
- Body mass index (BMI, kg/m²)
- Body mass index category (kg/m²) (< 25, ≥ 25)
- APOE allele status (ε2ε2, ε2ε3, ε2ε4, ε3ε3, ε3ε4, ε4ε4)
- Baseline cholinesterase inhibitors (AChEI) medication or memantine use (AChEI includes donepezil, rivastigmine, and galantamine)

6.2 Medical History

Medical history data for this study is transferred from Study M15-566 and will be conducted on Safety Data Set. The conditions/diagnoses recorded in medical/surgery history eCRF will be coded using the most current version of the Medical Dictionary for Regulatory Activities (MedDRA). Data will be summarized and presented using system organ classes (SOCs) and preferred terms (PTs). The SOC will be presented in alphabetical order and the PTs will be presented in alphabetical order within each SOC. The number and percentage of subjects with a particular SOC and PT will be summarized for each treatment group and overall. Subjects reporting more than one PT within a SOC will be counted only once for that SOC.

The following disease history variables will be summarized for each treatment group, and overall subjects.

- Age at onset of symptoms of cognitive impairment (years)
- Age when first diagnosed as having MCI due to AD or AD (years)

- Years since onset of symptoms of cognitive impairment (Date of Day 1 – Date of onset)
- Years since MCI due to AD or AD diagnosis (Date of Day 1 – Date of diagnosis)
- Family history of AD (None, biological mother, biological father, full sibling, biological child)
- Years of formal education

Categorical variables will be summarized with the number and percentage of subjects in each category. Continuous variables will be summarized with descriptive statistics (number of non-missing observations, mean, standard deviation, median, minimum, and maximum).

6.3 Previous and Concomitant Medications

Previous medications are defined as all medications with a start date before the first study drug infusion of M15-570, regardless of the end date of these medications. Concomitant medications are defined as all medications, other than study drug, taken during the treatment period (i.e., from the first day of study drug administration through 45 days after the last day of study drug administration). Concomitant medication use for AD or MCI will be summarized into two categories: taken both at baseline and post-baseline, not taken at baseline but taken post-baseline. Previous and concomitant medications will be coded using the World Health Organization (WHO) dictionary and will be summarized by generic name and Anatomical Therapeutic Chemical (ATC) classification system level 3. The number and percentage of subjects who take at least 1 medication and who take at least 1 dose of each specific medication in the following categories will be summarized for each treatment group and overall subjects.

- Previous AD or MCI medication: donepezil, rivastigmine, galantamine, tacrine, memantine, investigational medicine or other.
- Previous antipsychotic/neuroleptic medications
- Previous anticholinergic medications

- Previous sedatives/benzodiazepines
- Previous Parkinsonian medications
- Concomitant antipsychotic/neuroleptic medications
- Concomitant anticholinergic medications
- Concomitant sedatives/benzodiazepines
- Concomitant Parkinsonian medications
- Concomitant AChEIs (donepezil, rivastigmine, galantamine) or memantine for cognitive impairment.

7.0 Subject Disposition

For subjects who are enrolled in the study, the number and percentage of subjects in each enrollment disposition category (enrolled but not treated, prematurely discontinued and completed) will be summarized for each treatment group and overall subjects.

The number and percentage of subjects who prematurely discontinued study drug or prematurely discontinued from the study will be summarized by reason (primary or any reason) for each treatment group and overall subjects.

In addition, the following additional summaries will be presented for all enrolled subjects:

- The number and percentage of subjects who are enrolled at each site.
- The number and percentage of subjects who prematurely discontinued at each site.

8.0 Study Drug Exposure and Compliance

Study drug exposure will be summarized for each treatment group and overall subjects. Duration of exposure is calculated as the last study drug administration date minus the first study drug administration date + 30. Total subject years of exposure is calculated by summing the duration of exposure across all subjects and dividing this sum by 365 (1 year will be considered to be 365 days). The number and percentage of subjects who have

taken a total of infusions ≤ 6 , 7 to 12, 13 to 18, 19 to 24, 25 to 30, 31 to 36, 37 to 42, 43 to 48, 49 to 54, 55 to 60, and ≥ 61 will be summarized. In addition, duration of exposure will be summarized with descriptive statistics (number of non-missing observations, mean, standard deviation, median, minimum and maximum duration, and total years).

To evaluate impact of Coronavirus Disease 2019 (COVID-19) pandemic on study drug compliance, expected infusions (completers are expected to have 65 infusions, prematurely discontinued subjects are expected to have expected number of infusions based on discontinuation visit date) and infusions missed due to COVID-19 pandemic will be summarized for each treatment group and Overall (mean, minimum, maximum of expected infusions; mean, minimum, maximum of missed infusions, mean of the percentage of missed infusions relative to expected number of infusions will be tabulated) across all countries and by country.

At each scheduled dosing visit, the investigator will document whether the subject has received the entire dose infusion or not and the volume administered will be recorded in the eCRF if the entire dose is not administered. The percentage of the assigned dose administered will be calculated at each visit. The mean of this percentage across infusions for each subject will be obtained. The descriptive statistics (number of non-missing observations, minimum, mean, median, standard deviation, maximum) based on each subject's mean volume percentage of study drug infusion will be summarized for each treatment group and overall subjects.

9.0 Efficacy Analysis

9.1 General Considerations

No efficacy analysis will be performed for this study due to early termination of the study.

10.0 Safety Analysis

10.1 General Considerations

No comparisons between treatment groups (Studies M15-566/M15-570) of interest will be performed unless otherwise specified.

All other safety assessments that are taken no more than 45 days after the last dose of study drug will be included in the safety evaluation of the Treatment Period, and all safety assessments that are taken more than 45 days but not more than 20 weeks after the last dose of study drug will be included in the safety evaluation for the Post-treatment Follow-up Visit.

The Safety Data Set will be the data set for all safety data analyses.

10.2 Analysis of Adverse Events

All adverse events will be coded using the most current version of the Medical Dictionary for Regulatory Activities (MedDRA). A treatment-emergent adverse event (TEAE) is defined as any adverse event that begins or worsens in severity on or after the first study drug dose date and no more than 20 weeks after the last study drug dose date.

10.2.1 Adverse Event Overview

The number and percentage of subjects experiencing one or more adverse events in the following adverse event categories will be summarized for each treatment group and overall subjects.

- Any TEAE
- Any TEAE that was rated reasonable possibility of being related to study drug by the investigator
- Any severe TEAE
- Any serious TEAE
- Any TEAE that led to discontinuation of study drug

- Any fatal TEAE
- All deaths

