**6.1.3 Relationship to Study Drug**

The investigator will use the following definitions to assess the relationship of the AE to the use of study drug:

Reasonable Possibility	After consideration of factors including timing of the event, biologic plausibility, clinical judgment, and potential alternative causes, there is sufficient evidence (information) to suggest a causal relationship.
No Reasonable Possibility	After consideration of factors including timing of the event, biologic plausibility, clinical judgment, and potential alternative causes, there is insufficient evidence (information) to suggest a causal relationship.

For causality assessments, events assessed as having a reasonable possibility of being related to the study drug will be considered "associated." Events assessed as having no reasonable possibility of being related to study drug will be considered "not associated." In addition, when the investigator has not reported a causality or deemed it not assessable, AbbVie will consider the event associated.

[figure not shown]
If an investigator's opinion of no reasonable possibility of being related to study drug is given, an Other cause of event must be provided by the investigator for the SAE.

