4.0 Appendix

Table 22 List of tables and figures to be programmed

Table	Title
TABLE 14.1__1	SUBJECTS DISPOSITION (ALL ENROLLED SUBJECTS)
TABLE 14.1__2.1	ACCOUNTABILITY BY INVESTIGATOR (ALL ENROLLED SUBJECTS)
TABLE 14.1__2.2	SUMMARY OF REASONS FOR STUDY DISCONTINUATION (ALL ENROLLED SUBJECTS)
TABLE 14.1__2.3	SUMMARY OF REASONS FOR STUDY DRUG DISCONTINUATION (SAFETY DATA SET)
TABLE 14.1__2.4	LISING OF SUBJECTS WHO MISSED ≥ 3 STUDY DRUG INFUSIONS DUE TO COVID-19 PANDEMIC (Safety DATA SET)
TABLE 14.1__2.5	LISTING OF SUBJECTS NUMBERS, INVESTIGATIONAL SITE NAMES, AND VISIT INFORMATION FOR SUBJECTS WHO RECEIVED REMOTE VIRTUAL VISITS DUE TO COVID-19 PANDEMIC (SAFETY DATA SET)
TABLE 14.1__2.6	LISTING OF SUBJECTS NUMBERS, INVESTIGATIONAL SITE NAMES, AND VISIT INFORMATION FOR SUBJECTS WHO RECEIVED REMOTE VIRTUAL VISITS DUE TO COVID-19 PANDEMIC (SAFETY DATA SET)
TABLE 14.1__3.1	DEMOGRAPHIC CHARACTERISTICS - PART 1 (GENDER, RACE, ETHNICITY, AGE GROUPS AND BODY MASS INDEX GROUPS) (SAFETY DATA SET)
TABLE 14.1__3.2	DEMOGRAPHIC CHARACTERISTICS - PART 2 (AGE, WEIGHT, HEIGHT AND BODY MASS INDEX) (SAFETY DATA SET)
TABLE 14.1__3.3	DEMOGRAPHIC CHARACTERISTICS - PART 3 (ALCOHOL AND TOBACCO USE) (SAFETY DATA SET)
TABLE 14.1__4	SUMMARY OF BASELINE CHARACTERISTICS (ITT DATA SET)
TABLE 14.1__5.1	SUMMARY OF MEDICAL/SURGICAL HISTORY BY BODY SYSTEM AND CONDITION/DIAGNOSIS (SAFETY DATA SET)
TABLE 14.1__5.2	SUMMARY OF ALZHEIMER'S DISEASE HISTORY (SAFETY DATA SET)
TABLE 14.1__5.3	SUMMARY OF ALZHEIMER'S DISEASE FAMILY HISTORY (SAFETY DATA SET)
TABLE 14.1__6	SUMMARY OF PREVIOUS AND CONCOMITANT MEDICATION USE (SAFETY DATA SET)
TABLE 14.1__7.1	NUMBER OF SUBJECTS FOR STUDY DRUG INFUSIONS (SAFETY DATA SET)
TABLE 14.1__7.2	SUMMARY OF STUDY DRUG EXPOSURE (DAYS) (SAFETY DATA SET)
TABLE 14.1__7.3	SUMMARY OF MEAN VOLUME PERCENTAGE OF ADMINISTERED STUDY DRUG INFUSIONS (SAFETY DATA SET)

TABLE 14.1__7.4	SUMMARY OF TILOVANEMAB EXPOSURE AFFECTED BY COVID-19 PANDEMIC (SAFETY DATA SET)
TABLE 14.3__1.1	OVERVIEW OF TREATMENT-EMERGENT ADVERSE EVENTS AND ALL DEATHS (SAFETY DATA SET)
TABLE 14.3__1.2	NUMBER AND PERCENTAGE OF SUBJECTS WITH TREATMENT-EMERGENT ADVERSE EVENTS BY SYSTEM ORGAN CLASS AND PREFERRED TERM (SAFETY DATA SET)
TABLE 14.3__1.3	NUMBER AND PERCENTAGE OF SUBJECTS WITH TREATMENT-EMERGENT ADVERSE EVENTS ASSESSED BY THE INVESTIGATOR AS HAVING REASONABLE POSSIBILITY OF BEING RELATED TO STUDY DRUG BY SYSTEM ORGAN CLASS AND PREFERRED TERM (SAFETY DATA SET)

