TABLE 14.3__1.4	SUBJECTS WITH TREATMENT-EMERGENT ADVERSE EVENTS BY SYSTEM ORGAN CLASS, PREFERRED TERM AND MAXIMUM RELATIONSHIP TO STUDY DRUG (SAFETY DATA SET)
TABLE 14.3__1.5	SUBJECTS WITH TREATMENT-EMERGENT ADVERSE EVENTS BY SYSTEM ORGAN CLASS, PREFERRED TERM AND MAXIMUM SEVERITY (SAFETY DATA SET)
TABLE 14.3__1.6	NUMBER AND PERCENTAGE OF SUBJECTS WITH TREATMENT-EMERGENT ADVERSE EVENTS BY PREFERRED TERM IN DESCENDING ORDER OF INCIDENCE (SAFETY DATA SET)
TABLE 14.3__1.7.1	LISTING OF SUBJECT NUMBERS ASSOCIATED WITH EACH PT FOR ALL TREATMENT-EMERGENT ADVERSE EVENTS (SAFETY DATA SET)
TABLE 14.3__1.7.2	LISTING OF SUBJECT NUMBERS ASSOCIATED WITH EACH PT FOR ALL TREATMENT-EMERGENT ADVERSE EVENTS ASSESSED BY THE INVESTIGATOR AS HAVING REASONABLE POSSIBILITY OF BEING RELATED (SAFETY DATA SET)
TABLE 14.3__2.1.1	NUMBER AND PERCENTAGE OF SUBJECTS WITH SERIOUS TREATMENT-EMERGENT ADVERSE EVENTS BY SYSTEM ORGAN CLASS AND PREFERRED TERM (SAFETY DATA SET)
TABLE 14.3__2.1.2	LISTING OF SERIOUS ADVERSE EVENTS (SAFETY DATA SET)
TABLE 14.3__2.2.1	NUMBER AND PERCENTAGE OF SUBJECTS WITH TREATMENT-EMERGENT ADVERSE EVENTS LED TO DISCONTINUATION OF STUDY DRUG BY SYSTEM ORGAN CLASS AND PREFERRED TERM (SAFETY DATA SET)
TABLE 14.3__2.2.2	LISTING OF ADVERSE EVENTS THAT LED TO DISCONTINUATION OF STUDY DRUG (SAFETY DATA SET)
TABLE 14.3__2.3.1	NUMBER AND PERCENTAGE OF SUBJECTS WITH FATAL ADVERSE EVENTS INCLUDING EATHS BY SYSTEM ORGAN CLASS AND PREFERRED TERM (SAFETY DATA SET)
TABLE 14.3__2.3.2	LISTING OF FATAL ADVERSE EVENTS (SAFETY DATA SET)
TABLE 14.3__2.4	LISTING OF SUBJECT DEATHS (SAFETY DATA SET)
TABLE 14.3__3.1	NUMBER AND PERCENTAGE OF SUBJECTS MEETING CRITERIA FOR POTENTIALLY CLINICALLY SIGNIFICANT HEMATOLOGY (SAFETY DATA SET)
TABLE 14.3__3.2	LISTING OF SUBJECTS MEETING CRITERIA FOR POTENTIALLY CLINICALLY SIGNIFICANT HEMATOLOGY (SAFETY DATA SET)
TABLE 14.3__4.1	NUMBER AND PERCENTAGE OF SUBJECTS MEETING CRITERIA FOR POTENTIALLY CLINICALLY SIGNIFICANT CHEMISTRY (SAFETY DATA SET)

TABLE 14.3__4.2	LISTING OF SUBJECTS MEETING CRITERIA FOR POTENTIALLY CLINICALLY SIGNIFICANT CHEMISTRY (SAFETY DATA SET)
TABLE 14.3__5	SUMMARY OF C-SSRS (SAFETY DATA SET)
TABLE 14.3__6.1	SUMMARY OF NUMBER AND PERCENTAGE OF SUBJECTS PERTAINING CEREBRAL EDEMA, MICRO- AND MACRO-HAEMORRHAGES, WHITE MATTER HYPERINTENSITIES (SAFETY DATA SET)
TABLE 14.3__6.2	NUMBER AND PERCENTAGE OF SUBJECTS WITH PRESENCE AND INCREASING SEVERITY OF CEREBRAL OEDEMA (SAFETY DATA SET)

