10.2.2 Adverse Event Incidence

TEAE incidence will be summarized and presented using primary MedDRA system organ classes (SOCs) and preferred terms (PTs). The system organ classes will be presented in alphabetical order and the preferred terms will be presented in the alphabetical order within each system organ class. Subjects reporting more than one adverse event for a given MedDRA PT will be counted only once for that term. Subjects reporting more than one adverse event within a SOC will be counted only once for the SOC total. Subjects reporting more than one adverse event will be counted only once in the overall adverse event total.

The number and percentage of subjects experiencing one or more TEAEs will be summarized by PT for each treatment group and overall subjects. The PTs will be presented by decreasing frequency in overall subjects.

The number and percentage of subjects experiencing one or more adverse events in the following adverse event categories will be summarized by primary SOC and PT for each treatment group and overall subjects.

- Any TEAE
- Any serious TEAE
- Any TEAE that led to discontinuation of study drug
- Any TEAE assessed by the investigator to be Reasonable Possibility of Being Related to study drug

The number of subjects experiencing one or more TEAEs will also be summarized by maximum severity category (mild, moderate, severe and unknown) and primary SOC and PT for each treatment group and overall subjects. Subjects reporting more than one TEAE for a given PT will be counted only once for that term in the most severe category

reported. If a subject has an adverse event with unknown severity, then the subject will be counted in the severity category of "unknown" even if the subject has another occurrence of the same event with a severity present. The only exception is if the subject has another occurrence of the same adverse event with the most extreme severity – "Severe." In this case, the subject will be counted under the "Severe" category.

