The number of subjects experiencing one or more TEAEs will also be summarized by maximum relationship category (Reasonable Possibility of Being Related, No Reasonable Possibility of Being Related and Unknown), as assessed by the investigator, and primary SOC and PT for each treatment group and overall subjects. Subjects reporting more than one TEAE for a given PT will be counted only once for that term in the most related category reported. If a subject has an adverse event with unknown relationship, then the subject will be counted in the relationship category of "unknown," even if the subject has another occurrence of the same event with a relationship present. The only exception is that if a subject has another occurrence of the same adverse event with a relationship assessment of "Reasonable Possibility of Being Related." In this case, the subject will be counted under the "Reasonable Possibility of Being Related."

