10.2.3 Listing of Adverse Events

The following additional summaries of adverse events will be prepared.

- List of subject numbers associated with each PT for all TEAEs
- List of subject numbers associated with each PT for all TEAEs assessed by the investigator as Reasonable Possibility of Being Related.
- Listing of all serious adverse events
- Listing of all adverse events that led to discontinuation of study drug
- Listing of all fatal adverse events
- Listing of all deaths

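### Do the investigator-rated related-event counts, and the protocol's Day 1 neurological symptom sentence, leave adverse events uncounted?

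*SAP*

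**What the plan says.** **Causality.** Protocol 6.1.3 gives the investigator two ratings, reasonable possibility or no reasonable possibility, and adds that "when the investigator has not reported a causality or deemed it not assessable, AbbVie will consider the event associated". Three SAP outputs count only events that the investigator rated as related:

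- the overview row in 10.2.1, "Any TEAE that was rated reasonable possibility of being related to study drug by the investigator";
- the SOC and preferred-term (PT) summary in 10.2.2, "Any TEAE assessed by the investigator to be Reasonable Possibility of Being Related to study drug";
- the list in 10.2.3, "List of subject numbers associated with each PT for all TEAEs assessed by the investigator as Reasonable Possibility of Being Related".

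The statistical programming plan carries this into its output titles. Table 14.3__1.3, for example, is titled for "ADVERSE EVENTS ASSESSED BY THE INVESTIGATOR AS HAVING REASONABLE POSSIBILITY OF BEING RELATED TO STUDY DRUG".

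SAP 10.2.2 also plans a summary by maximum relationship (Table 14.3__1.4) with three categories: related, not related and unknown. Its counting rule is "Subjects reporting more than one TEAE for a given PT will be counted only once for that term in the most related category reported". On missing ratings it says "If a subject has an adverse event with unknown relationship, then the subject will be counted in the relationship category of" unknown, except where the subject has another occurrence of the same event rated as a reasonable possibility.

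**Day 1.** Protocol 5.3.1.1 (Neurological Examination) makes the Day 1 examination the baseline. It then assigns symptoms found on Day 1 to M15-566, and new or changed symptoms after Day 1 of drug administration to M15-570. Protocol 6.1.4 collects all adverse events from the time of study drug administration. The treatment-emergent definitions in Protocol 8.1.4.2 and SAP 10.2 both start on the date of the first dose, which is Day 1. SAP 5.0 limits the Safety Data Set to M15-570 data.

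**The concern.** Long-term safety is the primary objective, and SAP v2.0 drops the efficacy, PK and biomarker analyses, so the adverse event tables carry much of the report. Two things then look wrong.

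First, the protocol counts a missing causality rating against the drug and the headline related row does not. A reader wanting the number of subjects with any associated event in the 6.1.3 sense may not find it, and SAP 13.0 does not mention the difference.

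Second, the Day 1 sentence names no dosing boundary, although the neighbouring physical examination text does. Protocol 6.1 keeps subjects under observation for at least 30 minutes after each infusion, so a neurological symptom could begin after the drug is given and be seen the same day. Taken literally, the sentence would file it under M15-566 and so outside the Safety Data Set. For the placebo/2000 mg sequence, Day 1 is the first exposure to the drug.

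**Working it through.** The plan states no figure to reproduce on this point. The check is of the counting rules and of how the passages fit together.

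**Causality, within one preferred term.** SAP 10.2.2 ranks related (R) above unknown (U) above not related (N). A subject's ratings for one term form a non-empty subset of {R, U, N}, which gives 2³ − 1 = 7 patterns.

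- Investigator-rated rule (contains R): 4 patterns.
- Protocol 6.1.3 convention (contains R or U): 6 patterns.
- R + U cells of Table 14.3__1.4: the same 6 patterns.

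The first two rules differ only for {U} and {U, N}. Running through all 3 + 9 + 27 + 81 = 120 ordered sequences of one to four ratings also gives 0 disagreements between the R + U cells and the 6.1.3 convention. The term-level count on the protocol convention can therefore be read from a planned table.

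**Causality, across terms.** Take four subjects with two terms each:

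| Subject | Term A | Term B | R + U cells filled | Associated under 6.1.3 | In overview row |
|---|---|---|---|---|---|
| 1 | U | U | 2 | yes | no |
| 2 | R | U | 2 | yes | yes |
| 3 | N | U | 1 | yes | no |
| 4 | N | N | 0 | no | no |
| Total | | | 5 | 3 | 1 |

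Adding term rows gives 5, which is not the 3 subjects wanted. A total row that counts each subject once under the same ranking would show R = 1 (subject 2), U = 2 (subjects 1 and 3) and N = 1, so R + U = 3, which is correct. SAP 10.2.2 does provide for an overall adverse event total that counts each subject once. It writes the relationship ranking at term level, so the documents leave open whether Table 14.3__1.4 will show that total by relationship.

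**Size.** One reclassified subject moves a percentage by 100/n:

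- 100/453 = 0.22 points overall, at the maximum in SAP 4.3;
- 100/400 = 0.25 points, at the planned enrolment in the protocol synopsis;
- 100/100 = 1.0 point in placebo/2000 mg, at the parent study's planned placebo arm (Protocol 3.0).

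The documents give no rate of missing causality. As an assumption, let each event lack a rating independently with probability q. A subject with m events, none rated related, then has at least one missing rating with probability 1 − (1 − q)^m. For m = 3 to 10 this is 0.3% to 1.0% at q = 0.001, and 5.9% to 18.3% at q = 0.02.

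**Day 1.** The passages side by side:

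| Onset | 5.3.1.1, literal | 5.3.1.1, as the baseline examination | 6.1.4 |
|---|---|---|---|
| Day 1, before infusion | M15-566 | M15-566 | M15-570 only if an SAE or protocol-related |
| Day 1, after infusion | M15-566 | not addressed | M15-570 |
| Day 2 onward | M15-570 | M15-570 | M15-570 |

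The readings part only in the middle row. Three things favour the baseline reading: the sentence follows the one naming the examination as baseline, Protocol 5.1 puts baseline procedures before the infusion, and SAP Table 2 (footnote f) puts the adverse event assessment before it too. On that reading 6.1.4 settles the row without conflict. The sentence also does not say that only symptoms after Day 1 belong to M15-570.

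**The case for a change.** The best case for acting runs as follows. The 6.1.3 sentence is written for causality assessments generally and is not confined to expedited reporting. The SAP foresees missing ratings, since it creates a category for them, yet specifies no subject-level figure that treats them as associated. On Day 1, Appendix C waives the neurological examination if it was done at Week 96 of M15-566, so some subjects may have no Day 1 examination for the sentence to attach to. Post-dose contact that day is planned, through an ECG and the observation period. The remedies would be cheap: one row, two footnotes, a clarified sentence and a date check.

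Part of this stands. The Day 1 sentence is loosely worded, and a subject-level count on the 6.1.3 convention is not guaranteed. But 6.1.3 describes how the sponsor regards an event. Protocol 8.1.4.2, which sets out the adverse event tables, does not invoke it, and the synopsis asks only for a breakdown by possible relation to study drug, which the SAP supplies. No planned analysis was dropped, so SAP 13.0 had nothing to declare. It also goes too far to say that no subject-level figure will exist, because the total row may provide it. As for the waived examination, a symptom first seen after the infusion is an ordinary adverse event under 6.1.4 whether or not an examination took place. The date check would need M15-566 records and collection rules that are not in these documents.

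**Conclusion.** No change follows on either point.

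The related-event rows are investigator-rated and say so. Missing ratings are displayed rather than absorbed into not related, and the term-level count on the protocol convention is the sum of two planned cells. An extra overview row would be a presentational preference and would correct no wrong number.

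The Day 1 sentence is a drafting looseness that sites and analysts would resolve sensibly from its context and from 6.1.4. The study has ended early (SAP 9.1), so rewording a site instruction now would have little effect.

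The size is 100/n per affected subject, at least 0.22 points overall, since SAP 4.3 caps enrolment at 453. That holds for any reclassified subject and is not evidence that one exists; the number affected may be zero. The conclusion assumes that the Day 1 sentence refers to the pre-dose baseline examination, which the context supports but the text does not state. It does not depend on whether Table 14.3__1.4 carries a total row by relationship, because the existing rows are correct as labelled either way.
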